## General Risks Related to Vaccination

In general, IM injection may cause local itching, warmth, pain, tenderness, erythema/redness, induration, swelling, arm discomfort, or bruising of the skin. Participants may exhibit general signs and symptoms associated with IM injection of a vaccine and/or a placebo, including fever, chills, rash, myalgia, nausea/vomiting, headache, dizziness, arthralgia, general itching, and fatigue. These side effects will be monitored but are generally short-term. Instructions regarding use of antipyretic medication can be found in Section 6.8.

Syncope can occur in association with administration of injectable vaccines. Syncope can be accompanied by falls. Procedures should be in place to avoid falling injury. If syncope develops, participants should be observed until the symptoms resolve. Fear of injection might lead to fainting and fast breathing.

Participants may have an allergic reaction to the vaccination. An allergic reaction may cause a rash, urticaria, or even anaphylaxis (see above risks related to Ad26.COV2.S). Severe reactions are rare. Participants with a known allergy, or history of anaphylaxis or other serious adverse reactions to vaccines or their excipients (including specifically the excipients of the study vaccine), will be excluded from the study.

After each vaccination, participants will remain at the study site for at least 15 minutes to 1 hour depending on the vaccination being administered (see SoAs for details) and will be closely observed by study staff. Necessary emergency equipment and medications must be available in the clinic to treat severe allergic reactions.

## Pregnancy and Birth Control

The effect of the study vaccine on a foetus or on nursing baby is unknown.

Women of childbearing potential will be required to agree to practicing a highly effective method of contraception and agree to remain on such a method of contraception from signing the informed consent form (ICF) until 3 months after the last dose of study vaccine (See Section 5.1, Inclusion Criteria). Women who are pregnant or breast-feeding will be excluded from the study. Women who become pregnant while enrolled in the study will not receive further study vaccine but may continue other study procedures at the discretion of the investigator (see Section 7.1, Discontinuation of Study Vaccination).

Applicable to the US only: Following local approval of protocol Amendment 15, participants who are pregnant may receive ad hoc booster vaccination with Ad26.COV2.S, if allowed by local regulations and if the investigator considers that the potential benefits outweigh the potential risks to the mother and fetus (See Section 8.7).

## Risks from Blood Draws

Blood draws may cause pain, tenderness, bruising, bleeding, dizziness, vasovagal response, syncope, and rarely, infection at the site where the blood is taken.

## Risks from Collection of Nasal Swabs

Collection of a nasal swab may cause a nosebleed.

## Theoretical Risk of Enhanced Disease

Vaccine-associated enhanced disease has been described for SARS-CoV and MERS-CoV in some animal models, and is associated with non-neutralizing antibodies and a Th2-skewed immune response. In contrast, the Ad26-based vaccines have been shown to induce a clear Th1-skewed immune response and generate potent neutralizing antibody responses in both humans and animal models (see Section 2.2). Participants in the present study will be informed of the theoretical risk of disease enhancement in the ICF. The initial cohort in this study (Cohort 1a) will include healthy adults aged  $\geq 18$  to  $\leq 55$  years of age. As a risk mitigation strategy, all participants in the study will be passively and actively monitored for acquisition of molecularly confirmed COVID-19 (see Section 4.1, Section 8.1.2, and Section 10.8, Appendix 8, Case Definitions for COVID-19). This active and passive surveillance system for detection of COVID-19, with influenza serving as a control to monitor the effectiveness of the surveillance system, will ensure rapid identification of COVID-19 and will ensure that appropriate treatment procedures can be initiated to reduce the risk of enhanced disease if it should occur. Selected members of the statistical programming and the statistics group will receive individual level unblinded data pertaining to study VAC31518COV1001 when unblinding at the participant level is required. They will monitor the number and severity of molecularly confirmed COVID-19 cases in the Ad26.COVID2.S and placebo groups to identify an imbalance between groups if it occurs. They will inform the Data Review Committee (DRC) as soon as an imbalance between groups is detected. A prespecified threshold (imbalance above a certain percentage and/or number of cases) that will trigger notification of the DRC will be described in the Statistical Analysis Plan.

## Risks from Optional Lymph Node Aspiration

Most common risks and discomforts associated with fine needle LNA include swelling, pain, tenderness, bruising and soreness at the procedure site. These symptoms usually do not last long (1 to 2 days). Rare side effects include developing an infection, or damage to surrounding nerves or blood vessels.

## Unknown Risks

There may be other risks that are not known. If any significant new risks are identified, the investigators and participants will be informed.

### **2.3.2. Benefits of Study Participation**

Participants may benefit from clinical testing and physical examination.

The efficacy, immunogenicity, and safety data to date support a favorable benefit-risk profile for Ad26.COV2.S in the proposed indication, ie, active immunization to prevent COVID-19 caused by SARS-CoV-2 in adults  $\geq 18$  years of age. The overall benefit and risk balance for individual participants is ongoing.

Preliminary immunogenicity and safety data for a Ad26.COV2.S booster dose ( $5 \times 10^{10}$  vp) at  $\geq 6$  months post-primary single-dose Ad26.COV2.S administration and efficacy data for a 2nd dose of Ad26.COV2.S 2-3 months post-primary single-dose Ad26.COV2.S administration support a favorable benefit-risk profile in participants who received a single dose of Ad26.COV2.S.

### **2.3.3. Benefit-Risk Assessment of Study Participation**

Based on the available data and proposed safety measures, the overall benefit-risk assessment for this clinical study is considered acceptable for the following reasons:

- Only participants who meet all inclusion criteria and none of the exclusion criteria (specified in Section 5, Study Population) will be allowed to participate in this study. The selection criteria include adequate provisions to minimize the risk and protect the well-being of participants in the study.
- Safety will be closely monitored throughout the study:

In general, safety evaluations will be performed at scheduled visits during the study, as indicated in the [Schedule of Activities \(SoA\)](#)

After each vaccination, participants will remain at the study site for at least 15 minutes to 1 hour depending on the vaccination being administered (see SoAs for details) and will be closely observed by study staff. Necessary emergency equipment and medications must be available in the clinic to treat severe allergic reactions. Participants will use a diary to document solicited signs and symptoms. Details are provided in Section 8.2, Safety Assessments and Section 8.3, Adverse Events, Serious Adverse Events, and Other Safety Reporting.

The investigator or the designee will document unsolicited AEs as indicated in Section 8.2, Safety Assessments; Section 8.3, Adverse Events, Serious Adverse Events, and Other Safety Reporting; and Section 10.4, Appendix 4, Adverse Events, Serious Adverse Events, Product Quality Complaints, and Other Safety Reporting: Definitions and Procedures for Recording, Evaluating, Follow-Up, and Reporting.

From the time of local approval of protocol Amendment 11 onwards, TTS is considered an adverse event of special interest (AESI) (Section 8.3.6). Suspected AESIs (thrombotic events and/or thrombocytopenia [defined as platelet count below 150,000/ $\mu$ L]) must be reported to the sponsor within 24 hours of awareness. Suspected AESIs will be followed up as described in the Schedule of Activities in Section 1.3.8.

Any clinically significant abnormalities (including those persisting at the end of the study/early withdrawal) will be followed by the investigator until resolution or until clinically stable.

AEs related to the optional LNA procedure will be monitored.

- Several safety measures are included in this protocol to minimize the potential risk to participants, including the following:

Eligibility will be reassessed pre-vaccination on Day 1.

Clinical laboratory assessment (blood and urine) will be performed at screening, pre-vaccination at each day of vaccination (pre-dose 1 and pre-dose 2), and at the Day 7 post vaccination visit for the primary regimens (Day 8 and Day 64). Details are provided in Section 10.2, Appendix 2, Clinical Laboratory Tests.

In Cohorts 1a and 3, five sentinel participants will be evaluated for safety before extending enrollment in each cohort. The sentinel participants will be vaccinated at least 1 hour apart. A telephone call will be made to each of the sentinel participants on Day 2 (approximately 24 hours post-vaccination) to collect safety data. The blinded 24-hour post-vaccination safety data in these sentinel participants will be reviewed by the principal investigator (PI) and sponsor's study responsible physician (SRP). Randomization and vaccination of additional participants will be halted until this 24-hour sentinel safety evaluation is completed. Refer to Section 4.1, Overall Design, for further details. For Cohorts 1a and 3, the second vaccination will be administered to the sentinel participants first. The PI and SRP will also review blinded safety data from the 5 sentinel participants following the second vaccination but randomization and vaccination of participants will not be halted during this review.

For Cohorts 1a and 3, an internal DRC will review blindeda safety data following administration of the first vaccination to the first 15 participants. Refer to Section 4.1, Overall Design, for further details.

There are prespecified rules for all participants, that if met would result in pausing of further vaccinations, preventing exposure of new participants to study vaccine until the DRC reviews all safety data (see Committees Structure in Section 10.3, Appendix 3, Regulatory, Ethical, and Study Oversight Considerations).

Study vaccinations will be discontinued in participants for the reasons included in Section 7, Discontinuation of Study Vaccination and Participant Discontinuation/Withdrawal.

Contraindications to vaccination are included in Section 5.5, Criteria for Temporarily Delaying Administration of Study Vaccination.

---

a The DRC will review blinded data first but may review unblinded data if deemed necessary.

### 3. OBJECTIVES AND ENDPOINTS

A description of study cohorts is provided in Section [4.1](#).

Objectives	Endpoints
Primary 
 
To assess the safety and reactogenicity of Ad26.COV2.S at 2 dose levels, <math>5 \times 10^{10}</math> vp and <math>1 \times 10^{11}</math> vp, administered IM as a single-dose or 2-dose schedule in healthy adults aged <math>\geq 18</math> to <math>\leq 55</math> years and in adults aged <math>\geq 65</math> years in good health with or without stable underlying conditions.
 
	All participants* in Cohorts 1, 2, and 3: 
 
Solicited local and systemic AEs for 7 days after each vaccination in the primary regimen
 
Unsolicited AEs for 28 days after each vaccination in the primary regimen
 
 For the primary endpoint: Serious adverse events (SAEs) and adverse events of special interest (AESIs) from the first vaccination until 2 years after the second vaccination for Cohorts 1 and 3, and until 6 months after the primary regimen for Cohort 2
Secondary 
 
To assess the humoral and cellular immune response to Ad26.COV2.S
 
	Humoral Immune Response All participants* in Cohorts 1, 2, and 3: 
 
SARS-CoV-2 neutralization: SARS-CoV-2 neutralizing titers in serum measured by a virus neutralization assay (VNA [wild-type virus and/or pseudovirion expressing S protein])
 
SARS-CoV-2-binding antibodies measured by enzyme-linked immunosorbent assay (ELISA): Analysis of antibodies binding to the SARS-CoV-2 S protein.
 
 Cellular Immune Response A subset of participants* in Cohorts 1, 2, and 3: 
 
Th1 and Th2 immune responses as assessed by flow cytometry after SARS-CoV-2 S protein peptide stimulation of peripheral blood mononuclear cells (PBMCs) and intracellular staining [ICS] including CD4+/CD8+, IFN<math>\gamma</math>, interleukin [IL] 2, TNF<math>\alpha</math>, IL-4, IL-5, IL-13, and/or other Th1/Th2 markers.
 

Exploratory 
 
To further assess the safety and reactogenicity of Ad26.COV2.S at a dose level of <math>5 \times 10^{10}</math> vp administered IM as a single booster vaccination at 6 months, 12 months, or 24 months after the primary regimen in healthy adults aged <math>\geq 18</math> to <math>\leq 55</math> years
 
	All participants* in Cohort 2: 
 
Solicited local and systemic AEs for 7 days after each booster vaccination time point
 
Unsolicited AEs for 28 days after each booster vaccination time point
 
SAEs and AESIs until the end of the study
 
Following Amendment 16, booster vaccination at 24 months will not be performed
 

Objectives	Endpoints

 
To further assess the humoral and cellular immune response to Ad26.COV2.S in various regimens
 
	
Humoral Immune Response:
 
Exploratory analyses may include the following assays for a subset of participants* in Cohorts 1 and 3:
 
 
SARS-CoV-2 neutralization as assessed by alternative SARS-CoV-2 neutralization assays (different from the VNA used for the secondary endpoint).
 
Analysis of antibodies binding to SARS-CoV-2 S protein and the receptor-binding domain (RBD) of the SARS-CoV-2 S protein by Meso Scale Discovery (MSD) assay.
 
Adenovirus neutralization.
 
Functional and molecular antibody characterization (eg, avidity, Fc receptor interaction, antibody isotyping).
 
Epitope-specificity characterization for B- and T-cells.
 
Cytokine profiling: Analysis of cytokines, chemokines, and other proteins of the innate or adaptive immune response in the serum or plasma.
 
Passive transfer: Analysis of immune mediators correlating with protection against experimental SARS-CoV-2 challenge in a suitable animal model.
 
Analysis of neutralizing and binding antibodies against emerging SARS-CoV-2 virus lineages.
 
 
Cellular Immune Response:
 
Exploratory analyses may include the following assays for a subset of participants* in Cohorts 1, 2, and 3:
 
 
Single IFN<math>\gamma</math> and IL-4 enzyme-linked immunospot (ELISpot) assay after stimulation of PBMCs with SARS-CoV-2 S protein peptides.
 
Analysis of gene expression in cells stimulated with SARS-CoV-2 S protein peptides, or in unstimulated cells (ex vivo).
 
Cytokine profiling: Analysis of cytokines, chemokines, and other proteins of the innate or adaptive immune response in cells stimulated with SARS-CoV-2 S protein peptides, or in unstimulated cells (ex vivo).
 
 
A subset of participants* in Cohort 2 only:
 
 
Analysis of the phenotype of antigen-specific T and B cells, assessed by single cell analysis (on frozen or Smart tube-isolated PBMCs).
 

Objectives	Endpoints

 
To perform a preliminary analysis of vaccine efficacy in the prevention of molecularly confirmed COVID-19
 
	
 
The number of molecularly confirmed COVID-19 cases in Ad26.COV2.S versus placebo recipients in the overall study
 

 
To perform preliminary analysis of vaccine efficacy in the prevention of asymptomatic SARS-CoV-2 infection
 
	
 
The number of participants with positive non-S protein ELISA (eg, N ELISA), if such an assay can be developed, in the Ad26.COV2.S and placebo groups
 

 
To evaluate the presence of SARS-CoV-2 infection and the presence and severity of COVID-19 signs and symptoms
 
	
 
Presence and severity of COVID-19 signs and symptoms
 
Confirmation of SARS-CoV-2 infection by molecular testing
 

 
To examine the immune response in vaccinated individuals after natural infection and to explore other potentially informative biomarkers (eg, those associated with more severe disease)
 
	
 
Confirmation of SARS-CoV-2 infection by molecular testing
 
SARS-CoV-2 neutralizing titers in serum measured by a VNA (wild-type virus and/or pseudovirion expressing S protein)
 
SARS-CoV-2-binding antibodies measured by ELISA: Analysis of antibodies binding to the SARS-CoV-2 S protein
 
Functional and molecular antibody characterization
 
Analysis of gene expression by RNA transcript profiling
 

 
To explore the immune responses in fine needle LNA in Cohort 1b participants
 
	
 
Magnitude, phenotype, antigen specificity and subset distribution of immune and stromal cells in lymph nodes and peripheral blood
 
Molecular network analysis of functional regulation of T- and B-cell subsets in lymph nodes
 

\* Excluding Group 5 (placebo only) participants who received a single dose of  $5 \times 10^{10}$  vp Ad26.COV2.S at the time of unblinding, after EUA or approval in any country and local approval of protocol Amendment 10.

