## Study Duration

For Cohorts 1 and 3, the study duration from screening until the last follow-up visit will be approximately 15 months per participant. For these participants, the study consists of a screening period of up to 28 days, vaccinations on Day 1 and Day 57, and follow-up visits up to 12 months after the second vaccination (Target Visit Day  $422\pm21$  days). In case participants consent for the additional follow-up (see SoA in Section 1.3.9), the study duration from screening until the last follow-up visit will be approximately 27 months per participant. For these participants, the study consists of a screening period of up to 28 days, vaccinations on Day 1 and Day 57, and follow-up visits up to 24 months after the second vaccination (Target Visit Day  $787\pm21$  days).

For Cohort 2a, the study duration from screening until the last follow-up visit will be approximately 24 months per participant. In this case, the study would consist of a screening period of up to 28 days, vaccination on Day 1, a single booster vaccination at 6 months or 12 months after completion of the single-dose primary regimen on Day 1 and follow-up visits up to 24 months after completion of the primary regimen on Day 1 (Target Visit Day  $731\pm21$  days).

For Cohort 2b, the study duration from screening until the last follow-up visit will be approximately 24 months per participant. In this case, the study would consist of a screening period of up to 28 days, vaccinations on Day 1 and Day 57, a single booster vaccination at 6 months or 12 months after completion of the 2-dose primary regimen on Day 57, and follow-up visits up to 24 months after completion of the primary regimen on Day 57 (Target Visit Day  $787\pm21$  days). If the 2nd vaccination at Day 57 is not provided, then participants will discontinue the study (refer to Section 7.2).

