Group 5 (placebo only) participants who wish to receive a single dose of  $5\times10^{10}$  vp Ad26.COV2.S (ie, at the time of unblinding, after EUA or approval in any country and local approval of protocol Amendment 10), will discontinue from participation in the placebo groups (refer to Sections 7.4 and 8.6). This will reduce study duration for all Cohort 2 and for some of the Cohort 1 and 3 participants. For Cohorts 1a, 1b, and 3, the safety follow-up will end at Day 422 (ie, the initially planned study completion date) or 6 months after vaccination, whichever comes first. For Cohorts 2a and 2b, the safety follow-up will end 6 months after vaccination.

All eligible participants who wish to receive a single ad hoc booster dose of  $5\times10^{10}$  vp Ad26.COV2.S (ie, at the time of local approval of protocol Amendment 15), will discontinue from participation in their current schedules (refer to Sections 7.5 and 8.7). In this case, the safety and immunogenicity follow-up will end 6 months after the ad hoc booster vaccination.

For each cohort, if a participant is unable to complete the study, but has not withdrawn consent, is not lost to follow-up, or has not died, an early exit visit will be conducted.

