## Study Completion Definition

For Cohorts 1 and 3, a participant will be considered to have completed the study if he or she has completed assessments at Day 422. In case participants consent for the additional follow-up (see SoA in Section [1.3.9](#)), they will be considered to have completed the study if he or she has completed assessments at Day 787. Participants who prematurely discontinue study vaccine for any reason before completion of the last study visit will not be considered to have completed the study.

For Cohort 2, a participant will be considered to have completed the study if he or she has completed assessments at 12 months after completion of the last booster vaccination for any group. Participants who prematurely discontinue study vaccine for any reason before that time will not be considered to have completed the study.

Group 5 (placebo only) participants who wish to receive a single dose of  $5 \times 10^{10}$  vp Ad26.COV2.S (ie, at the time of unblinding, after EUA or approval in any country and approval of protocol Amendment 10), will discontinue from participation in the placebo groups (refer to Sections [7.4](#) and [8.6](#)). This will reduce study duration for all Cohort 2 and for some of the Cohort 1 and 3 participants. For Cohorts 1a, 1b, and 3, the safety follow-up will end at Day 422 (ie, the initially planned study completion date) or 6 months after vaccination, whichever comes first. For Cohorts 2a and 2b, the safety follow-up will end 6 months after vaccination. At that time, the participant will be contacted (phone call) by the site with regards to SAE and AESI collection, after which the participant will be considered to have completed the study.

All eligible participants who wish to receive a single ad hoc booster dose of  $5 \times 10^{10}$  vp Ad26.COV2.S (ie, at the time of local approval of protocol Amendment 15), will discontinue from participation in their current schedules (refer to Sections [7.5](#) and [8.7](#)). In this case, the safety and immunogenicity follow-up will end 6 months after the ad hoc booster vaccination.

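### The primary SAE/AESI endpoint for Cohorts 1 and 3 runs to 2 years after dose 2, but the base schedule collects events for only 12 months and makes the second year opt-in

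*Protocol*

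**What the plan says.** The Synopsis (1.1) and Section 3 set the primary SAE and AESI endpoint for "All participants* in Cohorts 1, 2, and 3". In Cohorts 1 and 3 it runs "from the first vaccination until 2 years after the second vaccination for Cohorts 1 and 3". The asterisk has one effect: "Excluding Group 5 (placebo only) participants who received a single dose of" the vaccine at unblinding.

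The follow-up provisions are shorter:

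- **Section 4.1, Study Duration:** the base schedule has "follow-up visits up to 12 months after the second vaccination" (Day 422). The longer schedule is conditional: "In case participants consent for the additional follow-up", then "the study duration from screening until the last follow-up visit will be approximately 27 months per participant" (Day 787).
- **Section 10.3.3:** the additional year requires reconsent.
- **Section 4.4:** for Cohorts 1 and 3, "a participant will be considered to have completed the study if he or she has completed assessments at Day 422". Day 787 is the completion point only for those who consented to more.
- **Section 8.3.1:** SAE reporting ends with the participant's last study-related procedure.
- **Sections 1.3.9 and 4.1:** a participant who takes the ad hoc booster leaves the schedule, and "the safety and immunogenicity follow-up will end 6 months after the ad hoc booster vaccination".

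On analysis, Section 9.4.2 summarises each adverse event as the percentage of participants with at least one occurrence. Section 9.7.1 censors safety analyses at unblinding or an unscheduled vaccine and lists later SAEs and AESIs. Section 9.8 adds the ad hoc booster as a censoring event.

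**The concern.** A primary endpoint names a time window and a population. Here the window is 2 years after dose 2 and the population is every Cohort 1 and 3 participant except the placebo crossovers. Nothing in the protocol makes the second year part of the base schedule, and nothing limits the endpoint to those who consent to it. The gap is planned non-collection, not dropout.

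At stake is what a 2-year primary safety result from this first-in-human trial would mean. Those who supply the second year are self-selected by two choices made after randomisation: consenting to more follow-up, and not taking the booster (or taking it late). A percentage of participants with an event, under a 2-year label, would put people with very different lengths of observation in one denominator.

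**Working it through.** **Reproducing the plan's day counts.** Dose 2 is on Day 57.

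- 57 + 365 = 422, and 57 + 730 = 787. Days 422 and 787 are 12 and 24 months after dose 2.
- With 28 screening days, (28 + 422)/30.4375 = 14.8 months and (28 + 787)/30.4375 = 26.8 months. These match the stated 15 and 27 months.

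**Participant who does not opt in.** Follow-up after dose 2 covers 422 − 57 = 365 of 787 − 57 = 730 days, or 50%. Counted from study start, 422/787 = 54%.

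**Participant who takes the ad hoc booster.** Under Section 4.1, follow-up ends at booster day + 182. This reaches Day 787 only if the booster is given on or after Day 787 − 182 = 605, which is 548 days (18.0 months) after dose 2. Target days are used and the ±21-day windows ignored. One qualification: Section 1.3.10 gives an extra safety visit after local approval of Amendment 16 to those who had already completed Booster FU2. Some of them are therefore observed for longer, by an amount the protocol does not tie to Day 787.

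**Where boosters might fall (assumed dates).** Suppose dose 2 was given between 29 June 2020 (original protocol date + 56 days) and 25 February 2021 (date of Amendment 10). Suppose the booster was given between 7 October 2021 (date of Amendment 15) and 120 days later. Booster + 182 days then falls about 13 to 25 months after dose 2. With dose 2 between 30 September and 31 December 2020, the range is about 15 to 22 months. Later local approval would move these later.

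**Share with the full window (illustration).** The protocol gives neither consent nor booster uptake. Let c be consent (assumed 0.6 to 0.9) and b booster uptake (assumed 0.3 to 0.7), taken as independent, with every booster given before Day 605. The share of booster-eligible participants reaching Day 787 is (1 − b) × c. It runs from 0.3 × 0.6 = 18% to 0.7 × 0.9 = 63%.

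**Detecting a rare event (illustration).** Table 14 gives 53% for at least one event at 1% incidence and N = 75: 1 − 0.99^75 = 52.9%. Read the 1% as a 2-year incidence at a constant rate, and let a whole group of 75 end at Day 422. The chance is then 1 − (1 − 0.01 × 422/787)^75 = 33.2%.

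**The case against.** The strongest defence is that this is a wording mismatch with limited consequences. The study is descriptive and tests no hypothesis. Section 9.5 bases the primary analyses of Cohorts 1a and 3 on safety data through Day 85, so those results are unaffected. Denominators under incomplete follow-up are normally left to the analysis plan. Boosted participants' later SAEs and AESIs fall under a separate primary endpoint for the booster. A simpler repair would keep 24 months and restrict it to those who consented.

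Much of this stands as a limit on the consequences. It does not remove the contradiction, because the endpoint's window and population are protocol content and an analysis plan cannot recover uncollected data.

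Three stronger readings are tempting but not supported:

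- **Two-year percentages biased low because Day 422 completers count as event-free for 2 years.** That is not quite the planned analysis. Sections 9.7.1 and 9.8 censor at unblinding, unscheduled vaccine or booster, and later events are listed or analysed separately. Those rules shorten the analysed window further, so the 2-year label fits even less well, but they do not produce that specific bias.
- **Active-to-placebo distortion of up to 787/422 = 1.9 from follow-up alone.** This needs every active participant to reach Day 787 and every placebo participant to stop at Day 422. The footnote already removes the crossovers. The remaining placebo participants have the same opt-in and are not eligible for the ad hoc booster.
- **Only active participants who consent and decline the booster can reach Day 787.** Consenting placebo participants who take no vaccine (Section 8.6), consenting participants ineligible for the booster, and those boosted from Day 605 onward can also reach it.

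The 33% figure is also limited. It assumes a constant rate, whereas Section 2.3.1 places the recognised vaccine risks early: TTS within 3 weeks and GBS within 42 days.

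**Conclusion.** The point stands as a contradiction in the current operative text. Sections 1.1 and 3 promise a 2-year primary SAE/AESI window for Cohorts 1 and 3, excluding crossovers. Sections 4.1, 4.4, 8.3.1 and 10.3.3 deliver 12 months plus an opt-in year, and the ad hoc booster is an exit from that year.

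The firm sizes come from day arithmetic: 365 of 730 days after dose 2 for anyone who does not opt in, and a shortfall under Section 4.1 for any booster before Day 605, subject to the extra visit noted above. The 18% to 63% range and the fall from 53% to 33% are illustrations under the stated assumptions. No claim is made about the direction or size of any bias between groups. The point matters mainly for the end-of-study analysis and should be corrected before it.

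**What to change.** Reconcile the endpoint in Sections 1.1 and 3 with Sections 4.1, 4.4, 9.7 and 9.8:

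1. Define the primary SAE/AESI window for Cohorts 1 and 3 as first vaccination to Day 422, keeping the crossover exclusion.
2. Report Day 422 to Day 787 separately, for participants who consented to the additional follow-up.
3. For both periods, give the number at risk and events per person-year. End person-time at the participant's actual end of follow-up or the censoring date under Sections 9.7 and 9.8, whichever is earlier.

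Step 3 is needed because a Day 422 label alone does not make the analysed follow-up complete: the same censoring can occur before Day 422.

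The cost is endpoint wording, one person-time table, and a primary claim of 12 months instead of 24. No type I error allocation is affected, since nothing is tested. Keeping 24 months but limiting it to those who consented would also make the text consistent, but the primary population would then be self-selected after randomisation.
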